Metabolomic profiling: In **SubAim 1b**, we will explore whether there are metabolites detected using untargeted metabolic profiling that enhance the Cho status score so that it better predicts Cho pool size as measured using isotope dilution. Broad-spectrum methods will be conducted by the NIH Common Fund Eastern Regional Comprehensive Metabolomics Resource Core (NIH C-F ERCMRC), under the direction of [name], by UPLC-TOF-MS and GC-TOF-MS (see letter of Support). The UPLC-TOF-MS method was adapted from the Human Serum Metabolome Consortium (HUSERMET) (93, 94). Briefly, plasma will be extracted, lyophilized, and reconstituted for UPLC-MS/MS analysis, and data will be acquired on an Acquity UPLC system coupled to a SYNAPT G2 Time of Flight (TOF) mass spectrometer (Waters Corporation, Milford, MA). Chromatographic separation of metabolites will be performed using reversed-phase chromatograph, as previously described (95). Broad-spectrum MS data will be processed using Progenesis QI for spectral alignment, deconvolution, peak picking, and matching to the ERCMRC in-house RT-MS library of approximately 900 metabolites and additional public databases, such as METLIN and HMDB. A list of ion intensities for each feature detected will be generated using retention time (RT) and m/z data pairs as the identifiers. Ion intensities for each detected peak will be normalized to the sum of the peak intensities (excluding standards) within that sample. The resulting normalized peak intensities contain a three-dimensional (3D) data matrix with RT, m/z, and ion intensities for each feature. Ion peaks are filtered based on the quality and reproducibility of the data in the pooled QC aliquots (see below). The ERCMRC uses a GC-TOF-MS broad spectrum metabolomics method developed by the Fiehn lab (96, 97). Briefly, plasma will be extracted, derivatized using a two-step procedure, and spiked with fatty acid methyl esters (FAMEs, as RI markers). Broad-spectrum GC-TOF-MS metabolomics data will be acquired on Pegasus GC x GC TOFMS (Leco Inc., St. Joseph, MI). Data files will be processed for deconvolution using ChromaTOF® software and transferred to BinBase (96, 98) for peak retention index calculations, metabolite identification, and generation of a table of peak identifications and intensities. Each peak intensity is normalized to the sum intensities of the metabolites and used for statistical investigation. In addition to BinBase, NIST library matches will be conducted. The ERCMRC has used these methods for analysis of plasma, serum, urine, feces, ovary, brain, saliva, sweat, breast tissue, muscle, kidney, and cells. System suitability checks will be performed before analysis of samples, to evaluate sensitivity, retention time, and mass calibration for tolerance within a pre-established range. In every analysis batch, at least 10% of the samples are QC standards, which are dispersed throughout the analytical run to evaluate any variability across or between plates. QC measures include reviewing the quality of each run, stability of internal standards signal, and drifts in retention time. All samples will be randomized prior to analysis to prevent potential bias towards diet periodss. In addition to analysis of each individual study sample, small aliquots of each of the dietary period study samples will be combined to create a pool, and then prepared in replicate. These quality control pools will be randomized with the individual study samples prior to data acquisition. For untargeted metabolomics analysis, an unsupervised multivariate analysis will be used to ensure that the QC pool samples cluster tightly and are in the center of the study samples from which they were derived (93, 95). If the QC pools do not cluster, the signals which introduce the variability will be removed from further analysis. After statistical and multivariate analysis are conducted which demonstrate which signals differentiate the study diet periods (described below), these QC pools (created for the diet periods) will also be used to obtain fragmentation patterns to identify the signals deemed important for distinguishing the diet periods.

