6 STATISTICAL CONSIDERATION

6.1 Primary Endpoint

SubAim 1a: Test assumptions used in the choline isotope dilution method for estimating choline pool size. In the subjects studied: a) collect urine after administration of deuterated choline and develop an estimate of % loss of administered label from body pool; b) measure choline pool size by isotope dilution and compare results

to changes seen using mass resonance spectroscopy (MRS) of choline compound peaks in liver (the major storage pool for choline); c) assess fatty liver by mass resonance imaging (MRI) and compare results to those obtained using Fibroscan methodology. These experiments will help us to refine the assumptions that we make to model choline pool size, and will validate the use of Fibroscan data as a measure of fatty liver.

SubAim 1b: Determine whether there are additional biomarkers from untargeted metabolomic profiling that, when added to the panel developed in Aim 1, are better at predicting choline status in people (using choline pool size determined by isotope dilution as a proxy for choline status). In the experiment described in Aim 1 we will add consideration of data from untargeted metabolomic profiles at the end of each diet period. This data will be used to identify metabolites that, when added to the biomarker panel developed in Aim 1, improve the correlation with choline pool size assessed using isotope dilution.

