6.3 Statistical Methods

Statistical methods (Aim 1, SubAim 1a,1b). Unsupervised principal component analysis will first be used to examine the clustering of samples from the diet periods, and to ensure that the QC pool replicates center in the samples from which they were derived. This will enable the evaluation of the stability of the platform across the plate and between days for the signals which have not yet been assigned, to remove any signals that are too random and prevent the desired clustering, and to identify subjects who outlie from their perspective diet periods. Supervised Orthogonal Partial Least Squares Regression (OPLS-R) will then be used to identify a panel of biomarkers, assign weight to each biomarker, and calculate a composite score to predict choline pool size. When we applied Orthogonal Partial Least Squares Effect Projections (OPLS-EP) and Orthogonal Partial Least Squares Discriminant Analysis (OPLS-DA) to our previous data, we identified a panel of biomarkers and calculated a composite score that successfully predicted choline status (baseline or depletion) for both men and women (**Figure 1**). In this proposed study, we will use OPLS-R instead of OPLS-DA, because choline pool size is a continuous variable, while choline status in our previous study was a categorical variable. We will analyze all of the samples using OPLS-R to identify a panel of biomarkers that predicts choline pool size universally for all three diet periods (healthy men, pre- and postmenopausal women). We will also consider performing the analysis for each diet period separately in case the universal panel does not provide high accuracy in prediction. For the purpose of validation, we will not split samples into training and testing sets, as it reduces the number of samples used for model building. Instead, prediction error will be estimated using the Bootstrap method, which was found by recent studies as providing “nearly unbiased estimates of future model performance without holding back data when making the final estimates of model parameters” (101). Variable Importance to Projection (VIP)

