score will be calculated based on the OPLS weights and the variability explained in OPLS-R. Biomarkers with $VIP > 1.5$ will be considered the most important biomarkers responsible for prediction. Pathway analysis will be performed using GeneGo metacore (Thomson Reuters, <https://portal.genego.com>) and QIAGEN's Ingenuity Pathway Analysis (IPA®, QIAGEN Redwood City, www.qiagen.com/ingenuity).

Statistical methods (SubAim 1c). Linear model with repeated measures will be used to identify SNPs that increase (or decrease) the risk for developing choline deficiency-induced organ dysfunction. This analysis will be performed for each diet period (healthy men, pre- and postmenopausal women) separately. In each linear model, the choline status score defined by Aim 1 is the response variable. Diet effect (fixed), genotype effect (fixed), subject effect (random) and diet \times genotype interaction effect are the independent variables. In the repeated measures design, each subject serves as his/her own control. Therefore, confounding effect from genotype is not our concern. However, it is possible that genotype serves as a moderator, which interacts with the diet effect, and affects the direction or strength of the diet effect. For example, the change in choline status score in responding to dietary choline may be observed in subjects with one genotype (responders), but not in subjects with other genotypes (non-responders). The genotypes that modify the diet effect will be identified by the diet \times genotype interaction term. This analysis will be performed in the MIXED procedure in SAS (SAS Institute, Inc., Cary, NC). Benjamini-Hochberg method for False Discovery Rate (FDR) correction will be used for multiple testing correction. To improve the normality of the data, data transformation such as log transformation will be applied to metabolomics data, and outliers with studentized residue > 3 or < -3 will be excluded. Post hoc comparisons will be performed to identify metabolites associated with different levels of dietary choline and different genotypes. The analysis described above will also be applied to choline pool size data to identify significant diet \times genotype interaction effect for choline pool size.

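### Section 6.3 does not require marker selection to be repeated inside the bootstrap and scored on left-out people, so SubAim 1b can report a gain from useless metabolites

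*Combined protocol and SAP*

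**What the plan says.** Section 6.3 fits the model to the full data set: "We will analyze all of the samples using OPLS-R to identify a panel of biomarkers". Markers with VIP above 1.5 are then labelled the most important. The synopsis (Efficacy Evaluations) adds a search for the smallest panel that reaches more than 90% accuracy. On validation, section 6.3 says "we will not split samples into training and testing sets, as it reduces the number of samples used for model building", and then "Instead, prediction error will be estimated using the Bootstrap method". It cites a regression textbook (reference 101) for the claim that the bootstrap is almost unbiased.

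Nothing further is specified. The type of bootstrap, the unit resampled and the steps repeated are not given, and the synopsis's statistical section does not mention validation. A random subject effect appears only in the SubAim 1c model.

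SubAim 1b, listed in section 6.1 under Primary Endpoint, is to "identify metabolites that, when added to the biomarker panel developed in Aim 1, improve the correlation with choline pool size". There is no minimum gain, no test and no rule for choosing the metabolites. Section 5.1 (Metabolomic profiling) words the aim more softly: "we will explore whether there are metabolites detected using untargeted metabolic profiling that enhance the Cho status score". Candidate features are matched to the "ERCMRC in-house RT-MS library of approximately 900 metabolites and additional public databases", and "Ion peaks are filtered based on the quality and reproducibility of the data in the pooled QC aliquots". Section 6.4 expects 150 completers analysed together, with a fallback to 50 per group.

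**The concern.** A bootstrap corrects only for the steps it repeats. If metabolites are first chosen on all the data because they track pool size, the people later left out have already helped to choose them. Out-of-bag error then looks better than it should.

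Optimism correction has a related weakness. It scores each resampled model on the full original sample, much of which trained that model, so it can under-correct when many candidates compete. Drawing samples instead of people adds a third route: a left-out sample may have the same person's other diet periods in the training set.

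SubAim 1b is the most exposed part of the plan. It compares a base panel with an extended one, and only the extended panel profits from a search among many candidates. With no hold-out and no minimum gain, the plan has nothing else that would expose a false improvement. The result could be a longer panel, reported as better, that predicts worse in new people.

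**Working it through.** **Plan's own figure.** The documents give no computed figure for Aim 1 or SubAim 1b to reproduce. The AUC of 98.77% in section 6.4 comes from the earlier 44-person study and cannot be recomputed here. The stated procedure was therefore simulated.

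**Inputs from the documents.** 150 people x 3 diet periods = 450 samples; fallback 50 x 3 = 150 samples; VIP > 1.5; about 900 library metabolites. QC filtering lowers that number and public databases can raise it.

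**Assumed and varied.** True R2 of the targeted panel 0.25, 0.5 or 0.8; 100, 300 or 900 useless candidates; within-person correlation (ICC) 0.3, 0.5 or 0.8. A high ICC cannot be taken for granted, since intake varies fourfold within each person (550/137.5 = 4).

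**Model.** Two-component PLS with one outcome, which predicts the same as OPLS with one predictive and one orthogonal component. There are 30 targeted markers, five of them informative. The extended panel is these 30 plus candidates with VIP > 1.5, refitted; the refit is an inferred reading of section 6.3. The reported change is r(extended) - r(base) under the same scheme. A false gain is a change above 0.05, a threshold chosen for this check. Each setting had 40 data sets with 10 resamples, and the truth came from 400 new simulated people. For 0 of 40 the upper 95% limit is 1 - 0.025^(1/40) = about 9%.

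**False gains out of 40, n=150** (each triple is ICC 0.3, 0.5, 0.8):

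| Scheme | R2 0.25 | R2 0.5 | R2 0.8 |
|---|---|---|---|
| A: selection fixed, samples drawn, out-of-bag; 900 candidates | 40, 40, 40 | 18, 26, 40 | 0, 0, 0 |
| A, 300 candidates | 32, 37, 40 | 0, 4, 19 | 0, 0, 0 |
| A, 100 candidates | 3, 7, 26 | 0, 0, 0 | 0, 0, 0 |
| A, 900 correlated candidates | 6, 20, 38 | 0, 0, 7 | 0, 0, 0 |
| A, 900, adding the 10 most correlated with the residual | 39, 40, 40 | 23, 31, 39 | 0, 0, 0 |
| B: selection repeated, people drawn, optimism correction; 900 | 37, 39, 40 | 0, 1, 14 | 0, 0, 0 |
| C: selection repeated, samples drawn, out-of-bag; 900 | 0, 2, 38 | 0, 0, 1 | 0, 0, 0 |

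Scheme D (selection repeated, whole people drawn, out-of-bag) gave 1 false gain in 3 x 3 x 3 x 40 = 1,080 VIP runs.

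**Reported against true r (scheme A, 900 candidates, ICC 0.5).**
- R2 0.25: reported 0.45 to 0.67 (+0.22); in new people 0.43 to 0.23 (-0.20).
- R2 0.8: reported 0.88 to 0.83 (-0.05); in new people 0.88 to 0.74 (-0.14). The loss is partly hidden, not reversed.
- R2 0.8 with the ten-feature rule: reported 0.88 to 0.89; true 0.88 to 0.86. Some gain, which is all the plan asks, appeared in 40 of 40 runs at every panel strength.

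**Second simulation, other settings.** True panel R2 about 0.52 to 0.59, 25 informative markers, people drawn, 30 data sets x 40 resamples, truth from 1,500 new people, 900 useless candidates, two components, ICC 0.5. Change in R2 (share of data sets above zero):

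| | n=150 | n=50 |
|---|---|---|
| True | -0.094 | -0.174 |
| Selection fixed, optimism correction | +0.081 (100%) | +0.208 (100%) |
| Selection repeated, optimism correction | +0.009 (63%) | +0.055 (90%) |
| Selection repeated, out-of-bag | -0.110 (0%) | -0.191 (0%) |

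At n=150, fixed selection with out-of-bag scoring also failed (+0.058), so repeating selection and scoring on left-out people are both needed. The average gain under repeated selection with optimism correction vanished with one component (-0.047), no within-person correlation (-0.036) or 300 candidates (-0.018), all at n=150.

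**Aim 1 panel.** Scheme A overstated R2 by at most 0.07 at n=150 where there was real signal, and by up to 0.20 at n=50 (R2 0.25, ICC 0.8). The highest reported Aim 1 R2 was 0.84 at n=150 and 0.88 at n=50.

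**The case against.** The plan nowhere says that selection stays outside the resamples. A reader might infer that section 6.3 prescribes a faulty bootstrap; the text does not support that. The cited textbook may itself require every modelling step to be repeated, which cannot be seen from these documents. The gap is one of specification, and the harm is conditional on how it is filled. That stands.

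A reader might also infer that the primary result is compromised, because SubAim 1b is listed in section 6.1. That does not follow. Section 2.1 defines the primary objective as the correlation of the Aim 1 score with pool size, and the universal Aim 1 panel is little affected. False attainment of the >90% goal is not shown.

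Large harm needs a weak or moderate panel and many useless candidates. Section 6.4 expects a strong panel, and at R2 0.8 no n=150 scheme gave a false gain above 0.05. Correlated candidates also reduce the problem. Against this, the synopsis (Efficacy Evaluations) expects smaller biomarker changes than in the earlier study, so a strong panel is not assured.

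The optimism-correction part is weaker than the fixed-selection part: at R2 0.5 and n=150 it is mixed. The .632 bootstrap with selection repeated was nearly safe in the second simulation (R2 change -0.131 to +0.002). Out-of-bag scoring is pessimistic, so it should not simply replace the Aim 1 accuracy estimate. These points limit the reach of the concern and shape the fix, but they do not remove the gap.

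**Conclusion.** The concern holds in conditional form and should be fixed. As written, section 6.3 permits analyses in which SubAim 1b reports a gain from useless metabolites while prediction in new people worsens.

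With about 900 useless, independent candidates, fixed selection reports some gain almost always for a weak or moderate panel (R2 about 0.25 to 0.5). The gain in r exceeds 0.05 in all runs at R2 0.25 and in roughly half to all at R2 0.5. Optimism correction with selection repeated misleads mainly with a weak panel or at 50 per group. With a strong panel at n=150, the VIP rule mostly hides part of a true loss. Drawing samples instead of people adds harm mainly at an ICC near 0.8.

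That the plan is silent on these steps is certain. The size of the harm rests on assumed panel strength, candidate number, ICC, number of components and the inferred refit.

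**What to change.** State in section 6.3:

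- **Unit.** Whole participants, with all their diet periods, are resampled or assigned to folds.
- **Steps repeated in each resample or fold.** Every coded step that uses pool size: VIP > 1.5 selection, number of components, reduction to the smallest panel, and addition of untargeted metabolites. Any removal of signals or subjects that uses diet period is repeated too, because diet is meant to drive pool size. Only QC filtering blind to both diet and pool size may be done once.
- **SubAim 1b.** The change in r and R2 is measured on left-out participants, not by optimism correction alone. A gain counts only if both rise and the extended panel's R2 is above zero. This matters at n=50: even under scheme D (R2 0.25, 900 candidates), R2 rose in 29, 34 and 44 of 60 runs because both panels averaged below zero. The combined rule leaves 0 to 2 of 60.
- **Aim 1 accuracy.** Prefer repeated, participant-grouped nested cross-validation. At n=150 it was within about 0.02 of the targeted panel's true R2. Out-of-bag scoring gave 0.78, 0.77 and 0.71 against 0.80, 0.80 and 0.78 in new people, and at n=50 with ICC 0.8 it gave 0.40 against 0.63. Repeats are needed because a single pass is noisy for the change in r (false gains in 0 to 3 of 60 at n=150 and 0 to 11 of 60 at n=50).
- **Fallback.** SubAim 1b results from 50 people are exploratory. The universal and separate models are reported side by side, without resampling that choice.

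The final model still uses all participants. The cost is SAP wording and computing time, with no extra participants or samples. The downside is that reported accuracy will look lower.

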Test Article(s) (If Applicable)	The experimental diets, delivering 100%, 50% (to be determined by a pilot study) and 25% of the recommended intake of Cho (in all forms) (550 mg Cho/70 kg body weight/d), are identical except for the bread that we offer (Cho in the bread will be varied to deliver the desired Cho above that delivered by the base 25% Cho diet as described previously (1)). On day 12 of a diet period, subjects will consume 250mg Cho in the form of Cho chloride (trimethyl-d9). We will confirm total Cho content of diets by LC-MS/MS analysis of samples of duplicate food portions as previously described (1).

Study Design	Healthy volunteers (n=50 males, 50 premenopausal females and 50 postmenopausal females; 30 additional subjects for dropout replacement), will be randomly assigned to an order of 2 week intervals of diets where they consume meals that we provide containing 100% of the recommended intake of Cho (550 mg Cho/day), 50% of the recommended intake of Cho (275 mg Cho), and 25% of the recommended intake of Cho (137.5 mg Cho) for 2 weeks each. Each dietary interval is followed by a minimum 2 week washout period. On day 12 of each diet period, subjects will consume a bolus of 250mg of Cho in the form of Cho chloride-(trimethyl-d9). Before this bolus, a plasma sample will be collected to measure baseline enrichment of Cho isotopes. At the end of each diet period, plasma and urine samples will be collected for biomarker assays and isotopic dilution estimation of Cho pool size, and we will perform transient elastography (Fibroscan) of liver to assess liver fat. (see Fig. 1, appendix).

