Efficacy Evaluations	
Expected Results and interpretation:
 
Our aim is to develop a panel of biomarkers and an algorithm for calculating a Cho status score that correlates well with measures of Cho pool size by isotope dilution. We will define the minimum set of biomarkers that provides >90% accuracy in predicting Cho pool size measured by isotopic dilution. We expect to see incremental declines in Cho status, as reflected in the panel of biomarkers. Results on the 100% diet should be similar to what we previously published. In the earlier studies, subjects were fed the 10% diet for a period of 2 to 7 weeks; in the proposed study, we feed 25%, 50%, and 100% (adequate intake) diets for two weeks (order randomly assigned) with 2 week washout periods in between. We expect that our results on the 25% & 50% diets will be less than those previously described; i.e. there will be smaller difference in the biomarkers than previously described. We expect that the 25% & 50% diets will show changes in Cho pool size and in biomarkers that fall between 100% and 10% values. Genotype will change the rate at which a diet treatment alters Cho pool size but will not affect whether our biomarker panel correlates with the pool size achieved. Thus, we do not have to power the study for genotype differences.

Pharmacokinetic Evaluations	N/A
Safety Evaluations	After each diet period a clinical chemistry panel will be run to assess potential liver and muscle damage. If any damage is noted after any of the dietary periods (liver damage = >1.5-fold increase in aspartate aminotransferase (AST) alanine transaminase (ALT) or muscle damage = >5-fold increase in creatine phosphokinase (CK)), affected subjects will follow the abnormal lab value protocol chart (See Appendix Figure 6). This will be reported to the IRB and the subject will be monitored and re-tested according to protocol and until AST/ALT and CK values return to normal.

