Genetic variation influences risk for becoming Cho depleted: Single nucleotide polymorphisms (SNPs) in several genes related to Cho and folate metabolism alter the risk for developing organ dysfunction when people become Cho depleted (25, 35, 51, 52). PEMT (phosphatidylethanolamine-N-methyltransferase) catalyzes the formation of Cho moiety as part of PtdCho (53) and this pathway can reduce the amount of Cho that must be obtained from the diet (3). This gene is induced by estrogen; with maximum induction at the concentrations achieved in women during pregnancy (54). Women with the C allele of *PEMT* rs12325817 (74% of Caucasian women) are more susceptible to liver damage when consuming a low Cho diet (51, 55) because this allele abrogates estrogen-induced expression of the gene (56). Other *PEMT* SNPs also increase Cho requirement (rs4646343-A and rs3760188-A) (52). A number of other common SNPs in genes related to choline metabolism alter the requirement for Cho (25, 35, 51, 52, 57-59). Thus, similar dietary intakes may lead to very different Cho status, depending on genotype.

Given the narrow range for healthy intake of Cho, given the establishment of a RDI/AI for Cho to maintain health, given the 3-fold variation in dietary intake in the US, given the effects of common SNPs on the dietary requirement for Cho, and because plasma Cho concentrations do not adequately reflect status (see below), it is important that a good biomarker panel for assessing Cho status be established.

Potential biomarkers for Cho status: Self-reported dietary intake is very hard to measure accurately, and

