3.1 Study Design

This is a crossover study wherein each subject will serve as their own control. Comparisons will be made between the low choline diet periods to the 100% choline diet at the beginning and end of the 6 weeks on the three dietary intervals (see Fig. 1, Appendix).

Screening: Before entry to the study the participants will be seen at the University of North Carolina Nutrition Research Institute Outpatient Clinical facility where a physical exam by a physician and a Clinical Chemistry panel will be performed to ascertain that they are healthy. Subjects will have mass resonance spectroscopy to measure Cho compounds in liver, and mass resonance imaging to assess fatty liver to validate the isotope dilution methodology and Fibroscan technology, respectively.

Intervention: Recruited subjects will be asked to fill out the Automated Self-Administered 24-hour Dietary Assessment Tool (ASA24) found on the NCI web site (<https://epi.grants.cancer.gov/asa24/>) for 3 days the week prior to the first diet intervention. This will estimate the choline intake level for subjects beginning the study. The week after screening, subjects will be placed on one of the three dietary choline levels (100%, 50%, and 25% - order randomly assigned) with a minimum 2 week washout between. On day 12 of each diet period, subjects will receive a 250mg bolus dose of the Cho delivered as Cho-d9 in order to estimate Cho pool sizes by isotope dilution (see Fig. 1, Appendix).

Follow-up: If the clinical laboratory data remain within normal values, this will conclude the subject's participation. If not, see section 4.3 (below).

Unscheduled Visits: Subjects may have to make unscheduled visits to pick up food if their freezer storage space is limiting.

3.2 Allocation to Treatment Groups and Blinding (if applicable):

All subjects will be randomly assigned to the order of the diet interventions. Investigators making metabolite, MRI, MRS, or Cho pool analyses will be blinded to diet assignments.

3.3 Study Duration, Enrollment and Number of Subjects:

The study lasts 10 weeks and a few days for each subject. We plan to enroll 150 subjects: 50 males, 50 pre-menopausal females, and 50 post-menopausal females. We will recruit an additional 30 subjects to account for drop out replacement, so the total number of subjects is 180.

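### With only a random subject effect, the diet × genotype P values run too small if the 100%-to-25% diet difference varies more between people than the other diet differences

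*Combined protocol and SAP*

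**What the plan says.** Section 6.3 (SubAim 1c) states that a "Linear model with repeated measures will be used to identify SNPs" that alter risk, with the choline status score as response. It lists the terms as "Diet effect (fixed), genotype effect (fixed), subject effect (random) and diet" × genotype interaction. "The genotypes that modify the diet effect will be identified by the diet" × genotype term. The model is fitted separately in men, premenopausal and postmenopausal women, and the same analysis is applied to choline pool size. On software, "This analysis will be performed in the MIXED procedure in SAS", but the section names no residual covariance structure, random diet slope, sphericity correction or degrees-of-freedom method. It does not say whether diet enters as a factor or as a dose. Benjamini-Hochberg correction and post hoc comparisons follow.

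Each subject receives three diets ("100%, 50%, and 25% - order randomly assigned", section 3.1). On timing, the synopsis says: "At the end of each diet period, plasma and urine samples will be collected for biomarker assays". That implies one score per subject per diet.

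On variation between people, the synopsis (Efficacy Evaluations) says "Genotype will change the rate at which a diet treatment alters Cho pool size", and section 1.1 concludes "Thus, similar dietary intakes may lead to very different Cho status, depending on genotype". The genotyping text in section 5.1 adds that estrogen slows depletion in some premenopausal women but not in others.

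**The concern.** A random subject effect with independent residuals gives every pair of diets the same correlation and every diet the same variance. The error for any difference between two diets is then one pooled quantity. The protocol's own account points elsewhere. If people deplete at different personal rates, their values spread out as intake falls, and the 100–25 difference varies more between people than the 50–25 difference. When one SNP is tested, the spread due to all other causes stays in the error. The pooled error is then too small for the 100–25 contrast and too large for the other two.

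At stake are the diet × genotype P values for score and pool size, any post hoc contrasts taken from the same model, and the small P values that feed the FDR correction and the pathway enrichment over more than 2 million SNPs (section 6.4).

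**Working it through.** **The plan's own figure.** Section 6.4 gives 89.61% power for an interaction effect of 0.6 at P<0.05. It does not state the N, genotype split, SD or sidedness, so the figure cannot be pinned down. A two-sided two-sample calculation with a 56/44 split gives 54% for 50 subjects and 84% for 100 women. The figure supplies no variance for the present question.

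**Inputs.** 50 completers per group (sections 3.4 and 6.4); three diets; one end-of-period score per diet; a SNP with no effect. *Assumed, because the documents give no variances:* residual variance 1, and a personal diet response proportional to the reduction in intake, with SD τ (in residual SDs) for the step from 100% to 25%.

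**Step 1: variances of the diet differences.** Put x = (100 − diet%)/75, so x = 0, 2/3, 1. A difference between two diets has variance 2 + τ²(Δx)²:

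- 100–50: 2 + (4/9)τ²
- 50–25: 2 + (1/9)τ²
- 100–25: 2 + τ²

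Compound symmetry uses their average, 2 + (14/27)τ².

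**Step 2: the 25%-versus-100% interaction contrast with pooled error.** Let k be the true variance divided by the pooled variance. In large samples the rejection rate at nominal 5% is 2Φ(−1.96/√k).

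| τ | 100–25 variance | pooled | k | large-sample rate | simulated, n=50 |
|---|---|---|---|---|---|
| 1 | 3.00 | 2.52 | 1.19 | 7.3% | 7.2% |
| 2 | 6.00 | 4.07 | 1.47 | 10.6% | 10.5% |
| 3 | 11.00 | 6.67 | 1.65 | 12.7% | 12.9% |

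The other two contrasts err the other way. At τ=3, 100–50 has variance 6.00 and 50–25 has 3.00, both below the pooled 6.67.

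**Step 3: the overall interaction test, diet as a 3-level factor.** The two within-subject components have variances in the ratio r = 1 + (14/27)τ², that is 1.52, 3.07 and 5.67.

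| τ | nominal 5% | nominal 0.1% |
|---|---|---|
| 1 | 5.1% | 0.11% |
| 2 | 6.0% | 0.29% |
| 3 | 6.9% | 0.51% |

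A separate check with 3 million draws gave 5.2%, 6.0% and 6.9% at 5%, and 0.13%, 0.30% and 0.48% at 0.1%. The ceiling at nominal 5%, as r grows without limit, is about 8.5%. The excess grows further into the tail: in large samples at nominal 5×10⁻⁸ it is about 15-fold at r=2 and 160-fold at r=5.

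**Step 4: person-to-person differences that are spherical.** With subject-specific diet responses of variance 0, 1, 4 and 9 times residual, spread equally over the diets, the overall test rejected in 5.0%, 4.8%, 5.0% and 4.9%.

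**Step 5: unstructured covariance.** The corresponding 2-df test held 4.8–5.2% at nominal 5% at every r tried, and about 0.1% at nominal 0.1%.

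**Step 6: cost in power.** Error degrees of freedom fall from 2×(50−2) = 96 to 50−2−1 = 47. If the covariance truly is spherical, an effect with 80% power on F(2, 96) has, on F(2, 47), about 79% at 0.05, 69% at 10⁻⁵ and 59% at 5×10⁻⁸.

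**The case against.** A reader might infer something stronger: that the model's null hypothesis is that nobody differs in diet response, so P values are too small whenever people differ. The documents do not support this. With one score per subject per diet, personal differences in response cannot be separated from residual error and already sit in the denominator of the interaction test. Step 4 shows the test stays at 5% however large those differences are, provided they are spherical. The condition that matters is unequal variance of the diet differences.

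The other side also has these points:

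- **The named test is little affected.** Section 6.3 identifies modifying genotypes by the interaction term, and the only powered SubAim 1c analysis is the PEMT test at P<0.05. This stands.
- **The stated hypothesis is untouched.** Section 6.2 expects a smaller pool or worse score at any given intake. That is a between-subject genotype effect, and it held 4.8–5.1% in simulation. This stands.
- **The contrast is not defined in the plan.** Section 6.3 announces post hoc comparisons but specifies neither a 25%-versus-100% interaction contrast nor its error term. The larger figures therefore apply only if such a contrast is taken from the pooled model.
- **The scan is declared exploratory and under-powered** (section 6.4), and section 10 defers genotyping. This limits the consequence. It does not make badly calibrated small P values harmless to FDR or enrichment.
- **Compound symmetry is implied rather than stated, and τ is assumed.** Both are true. The synopsis also expects smaller biomarker changes than in the earlier 10%-diet studies, so nothing in the documents establishes τ of 2 or 3.

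**Conclusion.** The point holds conditionally and is a cheap improvement. The listed terms imply compound symmetry, while the protocol's expectation of different depletion rates makes a more variable 100–25 difference plausible. If that is so, diet × genotype P values are anti-conservative. The effect is minor for the overall test at 5%, moderate for a pooled-error 25%-versus-100% contrast, and proportionally largest in the small-P tail used by the FDR step and the SNP scan.

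The sizes rest on assumed τ of 1 to 3, a dose-proportional response, 50 subjects per group, one score per diet and diet as a 3-level factor. They do not show that the PEMT result at P<0.05 would be materially wrong.

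**What to change.** In section 6.3, for both score and pool size:

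- Use one end-of-period value per subject per diet. Section 4.2 draws metabolomics on day 12 and again on day 15, and section 6.3 does not say which feeds the score. If both entered under a random subject effect, with subject × diet variance 0.5 to 2 times residual, simulated error at nominal 5% was 12% to 21%.
- Enter diet as a 3-level factor.
- Replace the random subject effect by an unstructured 3×3 within-subject covariance: REPEATED diet / SUBJECT=id TYPE=UN, with DDFM=KR on the MODEL statement.
- Take post hoc contrasts from that model.

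Adding a random diet effect at each factor level is not an alternative, because with one value per cell it cannot be separated from the residual.

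The change costs one line of code and some wording. If the covariance is truly spherical it also costs about 1 point of power at 0.05, and more at very small thresholds (Step 6), where the scan is already declared under-powered.
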